6.6.2.2 Phase 2a dose finding

Secondary efficacy endpoints include DOR, CBR, DCB, DCR, duration of disease control, TTP, TTR, TTNT, PFS, OS, MRD[-] CR rate, MRD[-] rate, and duration of MRD negativity.

DOR

DOR is defined in Section [6.6.2.1](#) and will be analyzed in the same way.

CBR

CBR is defined as the proportion of patients with a confirmed response of sCR, CR, VGPR, PR, or minimal response per IMWG criteria.

The analysis of CBR will be based on the safety population.

CBR will be summarized by frequencies, percentages, and 2-sided 95% exact binomial CIs.

DCB

DCB is defined as the time from the date of first documentation of a minimal response or better to the date of first documentation of confirmed progressive disease or death due to any cause, whichever occurs first. Patients without documentation of confirmed progressive disease or death will be censored at the censoring time point for PFS as specified in [Table 1](#).

DCB (months) = (earliest date of PD or death or censor – date of first minimal response or better + 1)/30.4375.

The analysis of DCB is based on a subset of safety population that only includes patients who have achieved a minimal response or better.

DCB will be summarized using KM method. The 25th, 50th (median) and 75th percentiles, alone with associated 2-sided 95% CIs based on Brookmeyer and Crowley method.

DCR

DCR is defined as the proportion of patients with a confirmed response of sCR, CR, VGPR, PR, minimal response, or SD per IMWG criteria.

The analysis will be based on the safety population.

DCR will be summarized by frequencies, percentages, and 2-sided 95% exact binomial CIs.

Duration of disease control

Duration of disease control is defined as the time from date of first documentation of SD or better to the date of first documentation of confirmed progressive disease or death due to any cause. Patients without documentation of confirmed PD or death will be censored following the same censoring rule for PFS as specified in [Table 1](#).

Duration of disease control (months) = (earliest date of PD or death or censor – date of first SD or better + 1)/30.4375.

The analysis of duration of disease control will include only patients who have achieved SD or better based on the safety population.

Duration of disease control will be summarized using KM method. The 25th, 50th (median) and 75th percentiles, alone with associated 2-sided 95% CIs based on Brookmeyer and Crowley method.

TTP

TTP is defined as the time the date of randomization to the first documentation of confirmed PD per IMWG criteria, or death due to PD.

TTP (months) = (earliest date of progression or death due to PD or censor – date of randomization + 1)/30.4375.

The analysis of TTP will be based on the ITT population.

TTP will be summarized using KM method. The K-M curves, the 25th, 50th (median) and 75th percentiles, alone with associated 2-sided 95% CIs based on Brookmeyer and Crowley method, and the K-M probability estimates with 95% CIs at 3, 6, 9 and 12 months (or later time points if applicable) will be presented. The number of patients with events and the number of patients censored will be summarized. Sensitivity analysis based on the safety population will also be provided.

TTR

TTR is defined as the time from the date of first dose administration of any study drug to the date of first documentation of confirmed PR or better.

The analysis of TTR will include only responders (PR or better) based on the safety population. TTR will be summarized using descriptive statistics with mean and 95% CI.

TTNT

TTNT is defined as the time from the date of first dose administration of any study drug to the date of the first dose initiation of the next line of anticancer therapy for any reason or death from any cause, whichever occurs first. Patients who neither started the next-line therapy nor die will be censored at the date last known to be alive before subsequent anticancer therapy. Patients who do not have any post-baseline follow-up assessments and who have not died will be censored at the date of first dose administration.

TTNT (months) = (earliest date of next line or death or censor – date of first dose + 1)/30.4375.

The analysis of TTNT will be based on the safety population.

TTNT will be summarized using KM method. The K-M curves, the 25th, 50th (median) and 75th percentiles, alone with associated 2-sided 95% CIs based on Brookmeyer and Crowley method, and the K-M probability estimates with 95% CIs at 3, 6, 9 and 12 months (or later time points if applicable) will be presented. The number of patients with events along with the type of events (death or next line of anticancer therapy) and the number of patients censored will be summarized.

PFS

PFS is defined as the time from the date of randomization to the date of confirmed disease progression or death due to any cause, whichever occurs first.

Censoring rule would follow [Table 1](#) except for replacing “the date of first dose” with “the date of randomization”.

PFS (months) = (earliest date of progression or death or censor – date of randomization + 1)/30.4375.

PFS would be analyzed in the same way as described in Section [6.6.2.1](#) based on the ITT population. Sensitivity analysis based on the safety population may also be provided.

OS

OS is defined as the time from the date of randomization to the date of death due to any cause.

OS (months) = (date of death or censor – date of randomization + 1)/30.4375.

OS would be analyzed in the same way as described in Section 6.6.2.1 based on the ITT population. Sensitivity analysis based on the safety population will also be provided.

MRD[-] CR rate

MRD[-] CR rate is defined in Section 6.6.2.1 and will be analyzed in the same way based on the safety population.

MRD[-] rate

MRD[-] rate is defined in Section 6.6.2.1 and will be analyzed in the same way based on the safety population.

Duration of MRD negativity

Duration of MRD negativity is defined in Section 6.6.2.1 and will be analyzed in the same way based on the safety population.

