6.6.1 Primary Endpoint Analysis

The primary efficacy endpoint for phase 2a is investigator-assessed ORR.

6.6.1.1 *Derivation of Endpoint(s)*

ORR is defined as the proportion of patients who achieved a confirmed response of PR or better per IMWG criteria.

6.6.1.2 *Main Analytical Approach*

Investigator-assessed ORR will be analyzed as the primary endpoint and calculated based on the safety population.

ORR at the primary analysis will be analyzed based on the confirmed responses, details of which is described as follows.

Confirmation of Response:

To confirm a response of sCR, CR, VGPR, PR, or MR, it requires 2 consecutive adequate assessments made at any time before the initiation of subsequent anti-cancer therapy. There is no requirement on the time interval between the two visits.

Below are some exceptions:

1. One or two consecutive occurrences of “not done” (ND) or “not evaluable” (NE) between responses can be skipped when confirming a response. For example,

PR → NE → PR: PR is considered to be confirmed in this case.

CR → ND → CR: CR is considered to be confirmed in this case.

2. Bone marrow assessments do not need to be confirmed.

Confirmation of PD:

It also requires 2 consecutive adequate assessments made at any time before the initiation of subsequent anti-cancer therapy to confirm PD. If only one PD value is recorded in the middle of responses better than PD, it will not be counted as a confirmed PD and therefore not an event for DOR, TTP, and PFS analyses. For example, the following case is not a confirmed PD:

BL → SD → PD → SD → SD → Subsequent anti-cancer therapy/End

Below are some exceptions:

- If only one PD is recorded as the last available assessment, then
 - 1) If this PD is due to imaging (plasmacytomas or bone lesion), then it can be considered as a confirmed PD.
 - 2) If this PD is the last available assessment prior to the subsequent anti-cancer therapy or is the reason for End of Treatment (EOT), then it can be considered as a confirmed PD.
 - 3) Otherwise, the PD is considered as unconfirmed.

Best Overall Response

Best overall response (BOR) is defined as the best response recorded after the first dose of study drug. The number and percentage of patients as well as corresponding 95% exact CIs with BOR in the following response categories will be summarized by dose level: sCR, CR, VGPR, PR, MR, SD, PD, and NE/ND. A list of investigator-assessed response at each visit will be provided.

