6.6.2 Secondary Endpoints Analysis

6.6.2.1 Phase 1 dose escalation

For the phase 1 dose escalation, secondary efficacy endpoints include ORR, DOR, PFS, OS, MRD[-] CR rate, MRD[-] rate, and duration of MRD negativity.

ORR

ORR is defined in Section [6.6.1.1](#).

The analysis of ORR will be based on the response-evaluable population.

ORR will be summarized by frequencies, percentages, and 2-sided 95% exact binomial CIs.

DOR

DOR is defined as the time from the date of first documentation of a confirmed PR or better to the date of first documentation of confirmed progressive disease or death due to any cause, whichever occurs first. Responders without documentation of confirmed progressive disease or death will be censored at the date of last adequate disease assessment. The censoring rule for DOR is the same as for PFS. Please refer to [Table 1](#) in Section [6.6.2.2](#) for the detailed censoring rules.

DOR (months) = (earliest date of progression or death or censor – date of confirmed response + 1)/30.4375

The analysis of DOR will only include confirmed responders (PR or better) based on the safety population.

DOR will be summarized using KM method. The K-M curves, the 25th, 50th (median) and 75th percentiles, alone with associated 2-sided 95% CIs based on Brookmeyer and Crowley method, and the K-M probability estimates with 95% CIs at 3, 6, 9 and 12 months (or later time points if applicable) will be presented. The number of patients with events along with the type of events (death or progressive disease) and the number of patients censored will be summarized.

PFS

PFS is defined as the time from the date of the first dose administration of any study drug to the first documentation of confirmed progressive disease or death due to any cause, whichever occurs first. Patients without documentation of confirmed progressive disease or death will be censored at the date of last adequate disease assessment prior to the date of initiation of subsequent anti-cancer therapy. Patients with no post baseline response assessment will be censored on day 1 unless patient died without extended loss-to-follow-up time. Determination of dates of PFS event and date for censoring is summarized in [Table 1](#) as follows.

Table 1: PFS Event and Censoring Method

Scenarios	Event date/censoring date	Event status
No (or inadequate) baseline tumor assessments ¹	Date of the first dose	Censored
No post-baseline assessments	Date of the first dose	Censored

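### DCB can include, and start from, a minimal response that was never confirmed, whereas CBR counts only confirmed responses

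*SAP*

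**What the plan says.** **The rate.** SAP 6.6.2.2: "CBR is defined as the proportion of patients with a confirmed response of sCR, CR, VGPR, PR, or minimal response per IMWG criteria". The rule that gives this meaning is in SAP 6.6.1.2: "To confirm a response of sCR, CR, VGPR, PR, or MR, it requires 2 consecutive adequate assessments", before any subsequent anticancer therapy. No interval between the two visits is required, and one or two consecutive visits recorded as not done or not evaluable may be skipped.

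**The duration.** In the same SAP section, "DCB is defined as the time from the date of first documentation of a minimal response or better" and ends at confirmed progression or death. The formula subtracts the "date of first minimal response or better". The population sentence reads: "The analysis of DCB is based on a subset of safety population that only includes patients who have achieved a minimal response or better". None of the three asks for confirmation of the response.

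**The protocol.** Section 13.1.3.2.2 has the same split: confirmation is required for CBR and not mentioned for DCB.

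**The contrast with DOR.** Protocol 13.1.3.2.1 and SAP 6.6.2.1 both define DOR from the first documentation of a confirmed PR or better, and both limit the analysis to confirmed responders. Only the formula's start is shorter: "date of confirmed response + 1)/30.4375".

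**Disease control.** "DCR is defined as the proportion of patients with a confirmed response of sCR, CR, VGPR, PR, minimal response, or SD per IMWG criteria", whereas "Duration of disease control is defined as the time from date of first documentation of SD or better". The confirmation rule does not list stable disease (SD).

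**The concern.** A duration endpoint is normally read beside its rate: this share of the arm had benefit, and in those patients it lasted this long. That reading requires the duration set to be the numerator of the rate. For ORR and DOR it is. For CBR and DCB the text does not make it so.

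Because both documents state the confirmation requirement for DOR, a programmer has good reason to treat its absence for DCB as deliberate and code the text as it stands. Two things follow. Patients with a single unreplicated MR enter the DCB Kaplan-Meier analysis although they are not in CBR. And a patient who is in CBR through a later confirmed response may have the DCB clock started at an earlier, isolated MR. The first tends to add short durations and the second lengthens some, so the net effect on the median cannot be predicted.

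**Working it through.** **Plan's own figures.** The documents print no figure for CBR or DCB. The printed table that uses the same denominator is the exact-interval table at 20 per arm (protocol 13.2, SAP 4.0). Clopper-Pearson limits for 12, 14 and 16 of 20 are 0.3605–0.8088, 0.4572–0.8811 and 0.5634–0.9427, which agree with the printed values. Nothing in that table depends on this point.

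**Rate and duration side by side**

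| | Confirmation stated in definition? | In formula start? | In analysis set? |
|---|---|---|---|
| CBR | yes | n/a | n/a |
| DCB | no | no | no |
| DOR | yes | yes (timing loosely worded) | yes |

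**Case 1: in DCB, not in CBR.** MR at one visit, then confirmed progression first seen 28 days later. There is only one MR assessment, so CBR does not count the patient. The literal DCB is (28 + 1)/30.4375 = 0.95 months, with an event.

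**Case 2: in both, but DCB starts early.** At successive 28-day visits: MR, SD, PR, PR. The PR is confirmed, so CBR counts the patient. The MR is not, because the next assessment is SD. The literal DCB starts at the MR, 56 days before the first PR, which adds 56/30.4375 = 1.84 months.

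**Size of the set mismatch.** With about 20 patients per arm, each Case 1 patient is 1/20 = 5 percentage points. For an assumed 1 to 2 such patients, the DCB set exceeds the CBR numerator by 5 to 10 points of the arm. CBR itself and its interval do not move.

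**DOR start date (wording only).** If the formula's date is the first documentation of the response later confirmed, as the definition says, the shift is 0. If it were coded as the confirming visit, then at 28-day visits:

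- next visit confirms: 28/30.4375 = 0.92 months
- one visit skipped: 56/30.4375 = 1.84 months
- two visits skipped: 84/30.4375 = 2.76 months

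These are nominal values. The SAP sets no interval, and visit windows and cycle delays can move them either way.

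**The case against.** The strongest reply is that the SAP is silent rather than permissive. It never says that an unconfirmed MR is accepted. Its confirmation rule names MR, which ORR does not need, so the rule must serve the MR-based endpoints. The SAP also omits the word elsewhere without meaning unconfirmed: the TTR population is described simply as responders, although TTR runs to a confirmed response. This shows what was probably intended. It does not settle what will be coded, because all three DCB statements omit the condition and the parallel DOR statements include it.

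One could argue the reverse: Appendix E asks for no second assessment for MR, so an unconfirmed start to DCB may be deliberate. But then CBR, which both documents define on confirmed responses, would use a different standard, and neither document says that this is meant.

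Three stronger readings are tempting and are not supported:

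- *All duration endpoints fail to match their rates.* DOR does match: its set is confirmed responders, as for ORR.
- *The DOR formula contradicts its definition.* The formula can be read as shorthand for an explicit definition. The duration of MRD negativity formula drops first documentation in the same way, and SAP Table 1 dates confirmed progression to its earliest date. This is an ambiguity that may amount to nothing.
- *Duration of disease control wrongly takes unconfirmed SD.* Neither the SAP's confirmation rule nor Appendix E asks for SD to be confirmed. Once a single SD counts in DCR, the SD mismatch disappears; only the word in the DCR definition is out of place.

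It also stands that the consequence is small. There are no hypotheses, decision rules or comparisons between dose levels, and protocol Appendix G records a sponsor decision not to proceed to phase 2a. The current protocol and SAP nevertheless still specify these endpoints.

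**Conclusion.** The point holds for CBR and DCB. As written in both documents, the rate requires confirmation and the duration does not, so a literal analysis can include patients outside the CBR numerator and can start the clock at an MR that was never confirmed. The size is 5 percentage points of the arm per affected patient at about 20 per arm. The number affected is unknown, and the range of 1 to 2 is only an illustration. The effect on the DCB median cannot be estimated from the documents.

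The DCR and DOR items are wording clean-ups. For DOR the ambiguity runs from 0 to about 2.8 months at nominal 28-day visits, and is not an established error. DCB and duration of disease control are descriptive secondary phase 2a endpoints. ORR, its interval and the sample size are untouched.

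**What to change.** In SAP 6.6.2.2:

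1. Limit DCB to patients counted in CBR. In the definition and the formula, start it at the first documentation of the MR or better that was later confirmed under 6.6.1.2.
2. Apply the same rule to MR-or-better responses in duration of disease control, and say whether an unconfirmed MR falls back to SD there.
3. Record both as changes from protocol 13.1.3.2.2. Protocol 13.1 requires deviations from its analyses to be indicated in the SAP.

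If unconfirmed MR is in fact intended for DCB, say so and report its count beside the CBR numerator.

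As clean-ups:

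4. Remove the confirmation requirement for SD from the DCR definition.
5. In SAP 6.6.2.1, write the DOR formula's start as the date of first documentation of the confirmed PR or better. Phase 2a reuses this definition, so one edit serves both phases.

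The cost is a few lines of text and a matching dataset specification. No new data are needed and no sample-size figure changes.

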## **9.11 Posttreatment Follow-up Assessments (PFS and OS)**

Patients who stop treatment for any reason other than progressive disease will continue to have PFS visits. The PFS visits should occur every 4 weeks from the EOT until the occurrence of progression, death, the start of subsequent systemic antineoplastic therapy, study termination, whichever occurs first. OS follow-up continues every 12 weeks until death, study termination, or patient withdrawal. Imaging tests for patients with extramedullary disease should be performed every 12 weeks or if new symptoms suggest progressive disease.

See the SOE ([Appendix A](#)) for appropriate assessments during follow-up.

NOTE: Treatment-related SAEs must be reported to the Global Pharmacovigilance department or designee. This includes deaths that the investigator considers related to study drug that occur during the posttreatment follow-up. Refer to Section [10.0](#) for details regarding definitions, documentation, and reporting of SAEs.

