### **DOR, DCB, Duration of Disease Control, TTP, TTNT, PFS, OS, and Duration of MRD Negativity for Patients Achieving MRD Negativity**

DOR and duration of MRD negativity are defined in Section [13.1.3.2.1](#).

DCB is defined as the time from the date of first documentation of a minimal response or better to the date of first documentation of confirmed progressive disease or death due to any cause, whichever occurs first. DCB will be calculated for only patients who achieved a minimal response or better. Patients without documentation of confirmed progressive disease or death will be censored at the date of last adequate disease assessment.

Duration of disease control is defined as the time from date of first documentation of SD or better to the date of first documentation of confirmed progressive disease or death due to any cause. Duration of disease control will be calculated for only patients who achieved SD or better. Patients without documentation of confirmed progressive disease or death will be censored at the date of last adequate disease assessment.

TTP is defined as the time from the date of randomization to the first documentation of confirmed progressive disease as defined by IMWG criteria. Patients without documentation of confirmed progression will be censored at the date of last adequate disease assessment. The analysis will be based on the ITT population.

TTNT is defined as the time from the date of first dose administration of any study drug to the date of the first dose initiation of the next line of anticancer therapy for any reason or death from any cause, whichever comes first. Patients who have not started the next-line therapy will be censored at the date last known to be alive before subsequent anticancer therapy. The analysis will be based on the safety population.

PFS is defined as the time from the date of randomization to the first documentation of confirmed progressive disease or death due to any cause, whichever occurs first. Patients without documentation of confirmed progressive disease or death will be censored at the date of last adequate disease assessment. The analysis will be based on the ITT population.

OS is defined as the time from the date of randomization to the documentation of death due to any cause. Patients without documentation of death at the time of analysis will be censored at the date last known to be alive. The analysis will be based on the ITT population.

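### The SAP's first-dose censoring rule for time to next treatment does not exempt patients who have already started next-line therapy, and the term that triggers it is undefined

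*SAP*

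**What the plan says.** SAP 6.6.2.2 starts the TTNT clock at first dose and stops it as follows: "date of the first dose initiation of the next line of anticancer therapy for any reason or death from any cause, whichever occurs first". The event does not depend on any assessment having been made. Two censoring sentences follow.

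- The first covers patients with neither event: "Patients who neither started the next-line therapy nor die will be censored at the date last known to be alive before subsequent anticancer therapy".
- The second reads: "Patients who do not have any post-baseline follow-up assessments and who have not died will be censored at the date of first dose administration".

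The derivation is "TTNT (months) = (earliest date of next line or death or censor – date of first dose + 1)/30.4375", and "The analysis of TTNT will be based on the safety population". One dose of any study drug is therefore enough to enter the analysis.

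Protocol 13.1.3.2.2 defines the same event: "date of the first dose initiation of the next line of anticancer therapy for any reason or death from any cause, whichever comes first". It has one censoring rule: "Patients who have not started the next-line therapy will be censored at the date last known to be alive before subsequent anticancer therapy". It contains no rule that censors at first dose.

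**The concern.** The second SAP censoring sentence names one of the two TTNT events (death) and omits the other (new therapy). A patient who is alive, has no qualifying assessment and has started new therapy is an event under the definition and censored under the sentence. Two programmers working from the same page could derive different data for that patient.

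The rule resembles the SAP's PFS convention. SAP 6.6.2.1 censors patients without a post-baseline response assessment on day 1 unless they died, and Table 1 footnote 3 censors at first dose when new therapy comes before any adequate assessment. That is coherent for PFS, where new therapy is a reason to censor. For TTNT, new therapy is the outcome.

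At stake are the earliest TTNT events, such as those following an early stop for intolerance. If they are dropped, the curve starts too high, and the planned table of events by type (death or next line) is wrong as well. Protocol 13.1 says departures from its analyses will be indicated in the SAP; this one is not flagged.

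**Working it through.** The plan gives no figure for this point, so the check is a comparison of texts followed by an illustration.

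**1. Does the wording conflict?** Take a living patient with no qualifying assessment who starts next-line therapy 30 days after first dose.

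| Rule | Status | TTNT (months) |
|---|---|---|
| SAP event definition | event | (30 + 1)/30.4375 = 1.02 |
| Protocol 13.1.3.2.2 | event | 1.02 by the same formula |
| SAP first-dose sentence, read literally | censored | (0 + 1)/30.4375 = 0.033 |

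The SAP formula takes the earliest of next line, death or censoring. A first-dose censoring date is always the earliest, so the formula does not restore the event.

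**2. What does the trigger mean?** The SAP does not define a post-baseline follow-up assessment. There are two readings.

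- *Disease assessments only.* In phase 2a the first scheduled one after baseline is Cycle 2 Day 1 (Protocol Appendix A, Table 3). Footnote x to Table 4 limits the bracketed disease tests at end of treatment to patients stopping for progression or in CR. A patient who stops in Cycle 1 for toxicity could then have none. For a living patient without new therapy, the rule also moves censoring from the protocol's last-known-alive date to first dose. Protocol 9.11 plans the follow-up that would be discarded: "OS follow-up continues every 12 weeks until death, study termination, or patient withdrawal".
- *Any follow-up.* Visits on Days 8, 15 and 22, the end-of-treatment visit or a survival contact would take nearly every such patient out of the rule.

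**3. Illustration.** The 3-month estimate is used because SAP 6.6.2.2 plans to report TTNT at 3, 6, 9 and 12 months. Inputs:

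- n = 20 per arm (SAP 4.0).
- k = 1, 2 or 3 affected patients, each starting new therapy 30 days after first dose (assumed).
- m = 0 or 4 other events at 60 days (assumed).
- Everyone else is event-free past 3 months (assumed).

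Formulas:

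- As defined: S(3) = (20 − k − m)/20.
- Literal SAP sentence: S(3) = 1 − m/(20 − k), because the k patients leave the risk set before any event.
- Standard error (SE) = √[S(1 − S)/20], with S as defined.

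| k | m | As defined | Literal | Shift (points) | SE (points) | Shift/SE |
|---|---|---|---|---|---|---|
| 1 | 0 | 95% | 100% | 5.0 | 4.9 | 1.0 |
| 2 | 0 | 90% | 100% | 10.0 | 6.7 | 1.5 |
| 3 | 0 | 85% | 100% | 15.0 | 8.0 | 1.9 |
| 1 | 4 | 75% | 78.9% | 3.9 | 9.7 | 0.4 |
| 2 | 4 | 70% | 77.8% | 7.8 | 10.2 | 0.8 |
| 3 | 4 | 65% | 76.5% | 11.5 | 10.7 | 1.1 |

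All six shifts are toward longer TTNT. The figures cover dropped events only, not the earlier censoring of living, untreated patients.

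**The case against.** The best defence is that the sentence is only loosely worded. It follows one limited to patients with neither event, and can be read as a sub-case that fixes a date when nothing is known after first dose. Elsewhere the SAP names the kind of assessment it means: response assessment in the PFS rule (6.6.2.1), disease assessment in the response-evaluable population (5.2). The different TTNT wording may mean any follow-up, in which case a patient known to have started new therapy has been followed and the conflict does not arise in practice.

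The route is also narrow. Phase 2a patients are seen on Days 8, 15 and 22 (Table 3). After an early stop they have an end-of-treatment visit, and Protocol 9.11 then provides PFS visits every 4 weeks until new therapy and survival contact every 12 weeks. In the single-agent study, Grade 3 or higher infusion reactions occurred in 2.1% of patients (Protocol 4.5.1.2), and at 1.5 mg/kg Q4W toxicities rarely led to discontinuation (4.1.2.2).

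Most of this stands as a limit on size. It does not remove the conflict, because the SAP neither defines the term nor confines the sentence to patients with neither event.

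A reader might go further and infer three things that the documents do not support:

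- *Every Cycle 1 toxicity stop followed by new therapy is lost.* That needs the disease-assessment reading, which the SAP does not state.
- *The shift is at least one SE in every case.* With four other early events it is 0.4 SE for k = 1 and 0.8 SE for k = 2.
- *Dose selection would be biased toward the less tolerable arm.* Nothing gives the count by arm. TTNT is one of 13 secondary efficacy endpoints, the SAP makes no formal comparison between dose levels (6.1), and the dose choice rests on integrated safety, efficacy, PK and PD data (Protocol 6.1).

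**Conclusion.** The point holds as a conflict in the SAP text. Followed literally, the first-dose sentence censors living patients who have had the TTNT event, contrary to the SAP's own definition and to the protocol. Whether anyone is affected depends on an undefined term. On the disease-assessment reading there are two consequences: lost early events, and censoring moved away from the protocol's last-known-alive date. On the any-follow-up reading there is little or none.

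The size is not known. The range of about 4 to 15 points at 3 months (about 0.4 to 1.9 SE) assumes 1 to 3 affected patients of 20, new therapy at 30 days, and zero or four other events at 60 days. The documents support none of these counts, and the true number is probably small. The effect is confined to a descriptive secondary endpoint of phase 2a. Protocol Appendix G records a sponsor decision not to proceed to phase 2a, within an amendment that was not implemented. The current protocol and the SAP retain phase 2a; if it is not run, there is no numerical effect.

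**What to change.** Replace the first-dose sentence in SAP 6.6.2.2 (TTNT) with:

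*Patients who have neither started next-line therapy nor died are censored at the date last known to be alive; those with no contact of any kind after first dose are censored at the date of first dose.*

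This makes new therapy an event whatever assessments exist, restores the protocol's censoring date and removes the undefined term. It also covers the preceding SAP sentence, which can then be deleted. If the sponsor wants to keep a rule tied to assessments, the SAP should define the term, exempt patients who have started next-line therapy, and flag the departure from Protocol 13.1.3.2.2.

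The cost is one sentence in the SAP and the matching line in the dataset specification. No new data are needed, since new-therapy dates, deaths and last-known-alive dates are already required for TTNT and OS.
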